The current 3D intraoral scanners capture the color of the oral tissues by emitting visible white light. A recently developed 3D intraoral scanner manufactured and CE marked by 3Shape A/S. Denmark, is also able to emit visible blue light (405 nm wavelength) (17) that allows capturing fluorescence from the oral tissues. Fluorescence is one of the most promising technologies for accurate detection of the early stages of enamel demineralization (18, 19, 20), but is currently available only in 1D or 2D devices. The main limitation of the existing devices featuring fluorescence, as already mentioned, is the challenge in comparing single images obtained at different points in time, which is at large influenced by imaging artifacts and noise. Imprecision in the comparison of these images compromises the ability to accurately monitor progressive demineralization of the dental hard tissues. To the best of our knowledge, there is no intraoral scanner reported in the scientific literature that combines fluorescence with 3D imaging. Thus, we hypothesize that this new intraoral scanner will benefit the monitoring of dental hard tissues and will aid dentists to identify early changes in tissue mineralization. With this method it is only possible to examine the tooth surfaces that are visible and directly exposed into the mouth (i.e. the smooth free surfaces and the occlusal fissures); the areas between the teeth (i.e. the approximal surfaces) cannot be visualized and therefore cannot be examined using the scanner.

3. Methods

Study execution

The participants will be monitored for a period of 1 year. The study will last approximately 2 years in total, with the baseline examination taking place in the beginning of 2019 and the last examination in the Spring – Winter 2020. Detailed plan of the study is shown in Table 1.

Information about the project

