A second appointment will be scheduled to conduct the oral health examination, including intraoral scanning and 2 bitewing radiographs (BW). The responsible researcher will request the participants to provide any recently available BW, in case these are not older than 6 months. No study-related examination will be conducted before the signed parental consent form has been obtained by the responsible researcher. The participants will not be offered any treatment other than routine professional tooth cleaning, which is important for a thorough visual examination and scanning of the teeth. In case any oral disease is detected, the participants will be referred to their dentist for treatment.

If no radiographs are available from the past six months, BW of the upper and lower posterior teeth on both sides will be taken. Since radiographs are part of the participants' annual dental check-up, these will be made available to the participants' dentist. Additionally, an oral examination will be conducted, and the condition of teeth, gums and fillings will be registered. The approximal plaque accumulation will be registered by employing the approximal plaque index (21). Thereafter, the teeth will be professionally cleaned, and the presence of caries lesions will be registered based on the visual and radiographic assessments. Caries lesions will be characterized as active or inactive and classified according to the ICDAS criteria into 7 stages (22). Furthermore, the presence of other visible defects on the oral hard tissues (*i.e.* erosive – abrasive lesions) will be registered using appropriate criteria (*i.e.* BEWE index for erosive tooth wear) (2, 23).

Subsequently, both the upper and lower jaw of the participant will be scanned using the intraoral scanner (Trios 4, 3Shape Trios A/S, Denmark). Scans will be obtained using visible white and blue light (wavelength 415 nm).

At the end of the session, the participants will be classified into different risk groups (low, moderate, high) according to the clinical findings and the information collected from the diet

history and the oral hygiene habits questionnaire (Appendix 1, 2). According to this classification, the responsible researcher will set the follow-up intervals for each participant (3-12 months). All patients will be monitored for 1 year.

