The same clinical procedures will be followed on the follow-up examinations (3 or 6 months) as well as on the final examination (1-year follow-up). The diet history, the oral hygiene habits questionnaire and the BW radiographs will be repeated only on the final examination (Table. 1).

4. Statistics

Paired T-test will be conducted to identify differences between the clinical scores at the baseline and the subsequent follow-ups for the different conditions investigated (*i.e.* caries score, erosion score) (24).

Exploratory analysis of the data extracted from the 3D scans will be conducted and compared to the clinical scores. Pearson correlation coefficients between the clinical scores and scores obtained from the 3D scans will be calculated. Paired t-test will be conducted to compare the number of lesions per patient (*i.e.* caries, tooth wear) that will be detected with the 2 different methods (scanning and clinical-radiographic examination).

All statistical analysis will be conducted using a 95% level of confidence.

Information regarding the sample size calculation using power analysis is provided on the following paragraph (§5. Research subjects - Sample size calculation)

5. Research subjects

The participants in this research project will be adolescents (12-16 years old) and young adults (18-19 years old) in Denmark and in Greece respectively.

As previously mentioned, this project will assess the ability of the intraoral scanner combining fluorescence to detect and monitor initial changes in the dental hard tissues, with special focus on caries: the most prevalent oral disease. The most important benefit expected by using the fluorescence method is the detection of initial lesions on dental surfaces directly exposed to the mouth. Fissure lesions in permanent posterior teeth usually appear in the long-lasting period of tooth eruption, *i.e.* from when the tooth first appears in the mouth until it contacts with the opposite dentition (28). Eruption of the first permanent molar starts around the ages of 6-8 years, the second molar at 12-14 years (28) and the third molar at 17-18 years. During the eruption period, the posterior teeth are at a higher risk for developing fissure caries. For the second permanent molars, this period can last up to 27 months form the first appearance in the mouth (~12 years old) (29) though for the third molars this period is usually longer.

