The initial state of the caries lesion is short-lived before progression of the disease. In older patients, caries lesions in fissures are either found at more advanced stages or they have already been treated by the dentist (*i.e.* sealed, filled or extracted as in the case of third molars) (28). Although initial caries lesions can be found in older patients, such initial lesions are located on the surfaces between the teeth, which are not visible to the intraoral scanner and therefore cannot be detected using this method.

For these reasons, the age group is set from 12 to 19 years. It is necessary to conduct the study on this group of young people, as the study is expected to benefit them directly. The same benefits are not expected if the study is conducted in older adults.

The early diagnosis of initial lesions in the young participants is more beneficial as it will allow the implementation of preventive measures to stop the progression of the disease. This will decrease the complexity of the treatments needed in the target group, as the initial lesions can be treated with minimal or non-invasive approaches. Thus, the economic burden for the state regarding treatment expenses of the adolescents and the individual costs related to future dental treatment will be reduced.

Inclusion criteria:

- Young people (12-19 years old) without chronic diseases.

Exclusion criteria:

- Participants in need of complex dental treatment (*e.g.* extensive restorative work, extractions, prosthetic treatment).
- Participants using partial/complete removable dentures or other appliances (*i.e.* orthodontic devices).

Sample size calculation

Caries data was used in order to calculate the desirable sample size for the current study, as that is the most prevalent oral disease in young patients and is widely investigated in epidemiological studies (1). Therefore, data regarding initial caries lesions was used for the sample size calculation, assuming that the new method will aid dentists to detect significantly more initial caries lesions compared to traditional methods.

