The study will be advertised at local schools and at the Dental Schools of the University of Copenhagen and the National and Kapodistrian University of Athens (on announcement boards and/or on the schools' webpages) and eventually giving presentations about the study by the responsible researcher. Further information regarding the informed consent and the in-person information meetings with the participants are provided on paragraph §3. Methods – Information about the project.

11. Research Ethics

The physical and mental integrity of the participants, as well as their privacy, will be respected. The good clinical practice (GCP) guidelines and EU General Data Protection Regulation (GDPR) will be followed.

Benefits of the Study

The risks, shortcomings and side effects (see above) are surpassed by the benefit of early diagnosis of oral diseases. The early diagnosis benefits the participants because oral problems can be treated more easily before they develop into more severe problems. The early detection of oral diseases is crucial, as often the problems can be treated non-invasively and different preventive strategies can be implemented to stop disease progression.

Additionally, the 3D intraoral scanner has the potential to aid dentists identifying changes in the oral tissues at earlier stages than with the visual – radiographic examinations. If this concretizes, the use of this equipment may potentially reduce the need for ionizing radiation for detecting oral problems and monitoring oral health, something that would be of significant benefit to all patients.

12. Participant compensation

This study is carried out on healthy persons under the direct responsibility of the dental school – University of Copenhagen. Thus, possible injuries to participants will be covered by the Danish "Patienterstatningen".

Hovedprotokol Version 3 Date: 8.1.2019

Table 1. Study Plan

Information meeting (~20 min)	Baseline examination January – September 2019 (~60 min)	3-month / 6-month follow-up examination (only for moderate/high risk groups) July 2019-March 2020 (~45 min)	1-year follow-up Final examination April – September 2020 (~60 min)	Study Termination September – December 2020

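### The scan is compared with a pooled visual-and-radiographic lesion count that includes approximal surfaces it cannot examine, so the total shows neither its gain on exposed surfaces nor whether it replaces radiographs

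*Combined protocol and SAP*

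**What the plan says.** All references are to the combined protocol and SAP.

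- **Section 3, Clinical and radiographic examination:** after cleaning, "the presence of caries lesions will be registered based on the visual and radiographic assessments".
- **Section 4, Statistics:** "Paired t-test will be conducted to compare the number of lesions per patient", for lesions "detected with the 2 different methods (scanning and clinical-radiographic examination". No breakdown by source of the finding or by tooth surface is described, for this test or for the correlations between clinical and scan scores.
- **Section 2b, Background:** "the areas between the teeth (i.e. the approximal surfaces) cannot be visualized and therefore cannot be examined using the scanner".
- **Section 5, Research subjects:** the initial lesions found in older patients are said to lie between the teeth, on surfaces "which are not visible to the intraoral scanner and therefore cannot be detected using this method".
- **Section 2a, Hypothesis 2:** the traditional methods to be improved on are visual-radiographic, named as one entity.
- **Section 11, Benefits of the Study:** the scanner may help in "identifying changes in the oral tissues at earlier stages than with the visual – radiographic examinations". The text continues: "If this concretizes, the use of this equipment may potentially reduce the need for ionizing radiation for detecting oral problems and monitoring oral health". It adds that this would benefit patients generally.

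**The concern.** The two counts cover different surfaces. The scan count can hold only lesions on surfaces the scanner sees. The comparator count can also hold approximal lesions. Their difference is a gain on exposed surfaces minus a loss fixed by the scanner's field of view, and the planned test reports only the net.

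This matters in two ways. If the net is positive, it meets the condition that Section 11 sets for its remark on radiation, although the scan may have found nothing that only bitewings show. If the net is null or negative, the study may report no benefit although the scan found more initial lesions on the exposed surfaces, which is the main benefit Section 5 expects. Neither result would tell a dentist what the scan adds where it can be used.

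**Working it through.** **The plan's own figure.** Section 5 gives mean 3.08 initial lesions, SD 1.23, a difference of 1 lesion, 5% significance, 90% power and n = 64. Two independent groups, two-sided: 2 × 1.23² × (1.960 + 1.282)² / 1² = 31.8, so 32 per group and 64 in total. The figure reproduces. The point below does not depend on it; it uses only the planning mean, the planning gain of 1 lesion and n = 64.

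**Decomposition.** Per patient, let V be the comparator lesions within the scanner's reach, A the comparator lesions outside it, and G the further exposed-surface lesions that only the scan finds. Suppose the scan finds all of V and none of A.

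- Comparator total = V + A
- Scan total = V + G
- Planned difference = G − A
- Exposed-surface difference = G

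The planned test estimates G − A. Hypothesis 2 can be informed by G only if A is known.

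**Assumptions for illustration.** The documents do not give A, so it is varied as a share of 3.08. Counts are independent Poisson with n = 64, a paired t-test at the two-sided 5% level and 4,000 simulated studies per case. None of this is in the documents.

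**(a) A positive total with nothing found outside the scanner's reach.** G is set so that the net gain is 0.5 or 1.0.

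| Share of 3.08 | A | G for net 0.5 | Studies favouring scan | G for net 1.0 | Studies favouring scan |
|---|---|---|---|---|---|
| 10% | 0.31 | 0.81 | 97% | 1.31 | 100% |
| 25% | 0.77 | 1.27 | 78% | 1.77 | 99.9% |
| 50% | 1.54 | 2.04 | 56% | 2.54 | 97% |

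In every cell the scan finds none of A. A significant total is therefore compatible with no replacement of what those lesions contribute to the comparator.

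**(b) A true exposed-surface gain hidden by the total.** G is fixed at 1.0, the planning effect. The variance of the difference is A + G, because V cancels, so the expected t is about (G − A) / (√(A + G) / √64).

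| Share of 3.08 | A | G − A | Expected t | Favouring scan | Favouring comparator |
|---|---|---|---|---|---|
| 10% | 0.31 | +0.69 | 0.69 / (1.144 / 8) = 4.8 | 99.8% | 0% |
| 25% | 0.77 | +0.23 | 0.23 / (1.330 / 8) = 1.4 | 27% | under 0.1% |
| 50% | 1.54 | −0.54 | −0.54 / (1.594 / 8) = −2.7 | 0% | 76% |

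The total difference is zero when A = G = 1, a share of 1 / 3.08 = 32%. In the same simulated studies, the comparison restricted to exposed surfaces favoured the scan in every run.

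**Visits.** Section 3 and Table 1 place bitewings at baseline and the final visit only, so the comparator contains no new radiograph at 3 or 6 months. Source labels would also make that difference visible.

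**The case against.** The strongest reply is that the comparator is the one Hypothesis 2 names, and that pooling is conservative: approximal lesions raise the comparator total and make a scanner advantage harder to show. Both points stand. They are reasons to keep the pooled test, but conservatism is exactly what can hide an exposed-surface gain.

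Several stronger readings are tempting and should not be made.

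- A reader might infer that the radiation saving is what justifies a study in minors. Sections 5 and 11 rest the case mainly on early diagnosis. The radiation sentence is an additional, doubly conditional remark and belongs to no objective or hypothesis.
- A reader might infer that the source of each lesion is lost. Section 3 does not describe the record form, and Table 1 lists the clinical and radiographic examinations separately. The form may already hold the source; what is missing is an analysis that uses it.
- A reader might infer that Section 11 claims the scanner works for approximal lesions or equally well in older adults. It says only that less radiation, if achieved, would benefit patients at large. That is loose beside Sections 2b and 5, both of which state the limit openly.
- A reader might want the study to measure how many approximal bitewing lesions the scan finds. Section 2b already settles that as none, so only bitewing-only lesions on exposed surfaces can be informative.

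**Conclusion.** The point holds as a gap in the analysis. As written, the lesion-count comparison yields a net figure that cannot be separated into a gain on exposed surfaces and a loss on approximal ones. A positive total does not bear on replacing radiographs, and a null or negative total does not exclude a real gain within the scanner's reach.

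The direction of the problem follows from Sections 2b, 3 and 4 alone. Its size is unknown. The documents give no visual/bitewing or surface split, and do not say how the 3.08 register lesions were detected. The tables show only what is possible under assumed shares of 10% to 50%, independent Poisson counts and a scan that finds every comparator lesion within its reach. They do not predict what this study will find. The comparison the plan specifies is not invalid; it is incomplete, and the remedy is inexpensive.

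**What to change.** 1. **Recording (Section 3).** Record each caries lesion by source (visual, bitewing, scan) and by surface (exposed or approximal) at baseline and 1 year. If the form already does this, say so. It should be in place at the examination, because source may not be recoverable from a merged record.
2. **Analysis (Section 4).** Keep the pooled comparison. Add, on exposed surfaces only, scan versus visual and scan versus visual plus bitewing. Report separately the number of approximal lesions outside the scanner's reach, and the proportion of bitewing-only lesions on exposed surfaces that the scan also found, with a 95% CI.
3. **Wording (Section 11).** Limit the remark that the scanner "may potentially reduce the need for ionizing radiation for detecting oral problems and monitoring oral health" to exposed surfaces, and reconcile its reference to patients generally with the limits in Sections 2b and 5.

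The cost is somewhat more detailed recording for three sources by surface, a short added analysis and a sentence of rewording. No extra visit, examination or radiation exposure is needed.

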For the sample size calculation, data collected by the Central Odontology Register of the Danish National Board of Health (Sundhedsstyrelsens Centrale Odontologiske Register SCOR) during the year 2017 from municipal dental clinics at 98 different municipalities in Denmark was used. According to the data, an average of 3.08 initial lesions, with a standard deviation of 1.23 were identified on 15-year old patients at the different municipalities. In this study, the desirable power was set on 90%, the level of significance on 5% and the effect size on 30% (1 lesion). By applying these parameters, the sample size was calculated to be 64 adolescents. Nevertheless, as a 10% drop-out is expected for this type of study, the final number of participants to be included in the study should be 70.

6. Risks, side effects and shortcomings in short and long term

Risks

This study will be conducted on healthy persons, on whom the procedures followed in this study are assumed to have a negligible risk.

No risk is related to the clinical visual examination.

Regarding the 3D intraoral scanning procedure, if the scan quality is poor and thus the scan is not useful for the research objectives, the scanning procedure should be repeated. This is of no risk for the patient but represents the inconvenience of a delay of the dental visit.

For the scanning using blue light (wavelength 415nm) possible risks exist. For the participant, light irritation of the mucosa and lips may result from a local, acute overexposure to the strong blue light. This irritation, though, is mild and temporary. For the operator, possible harm to the eyes, especially on the lenses and the retinal tissues, may be caused by long-term cumulative exposure to blue light. These risks are not particular for this specific intraoral device but are

common to any dental equipment that uses blue light. Having these risks in mind, the equipment will be used properly and with care: the exposure time will be limited to 15 seconds per tooth and direct exposure to mucous membranes will be avoided. The equipment will be started only after it has been inserted into the patient's mouth. The operator will avoid looking directly into the mouth and instead will look on the computer screen during the scanning procedure. Eye-protection goggles filtering light under 500 nm are suggested to be used by the operator.

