 Oral information about the clinical examination Distribution: Inform consent agreement Diet history registration form Questionnaire about oral hygiene habits 	 Registration of diet history and oral hygiene habits Clinical examination (registration of plaque, caries and other findings) Teeth cleaning Radiographic examination Scanning Participant risk assessment – Set follow-up intervals Data selection and management 	 Clinical examination (registration of plaque, caries and other findings) Teeth cleaning Scanning Data selection and management 	 Registration of diet history and oral hygiene habits Clinical examination (registration of plaque, caries and other findings) Teeth cleaning Radiographic examination Scanning Data selection and management 	 Data management Statistical analysis Publication

References

- 6) Mejàre I, Axelsson S, Dahlén G, Espelid I, Norlund A, Svensson Å, Tranæus S, Twetman S. The Swedish Council on Technology Assessment in Health Care. Karies diagnostik,
- riskbedömning och icke-invasiv behandling. En systematisk litteraturöversikt. 2007; 403p.

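### The scan reading is not kept independent of the clinical chart and no scan lesion rule is fixed in advance, so the two-method comparison is open to review bias

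*Combined protocol and SAP*

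**What the plan says.** **Order of events.** Under Clinical and radiographic examination (Section 3), after cleaning, "the presence of caries lesions will be registered based on the visual and radiographic assessments". Lesions are staged by ICDAS and erosive wear by BEWE. The next step is the scan: "Subsequently, both the upper and lower jaw of the participant will be scanned using the intraoral scanner". The same procedures are repeated at the follow-up and final visits, with radiographs again only at the final one.

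**Who sees what.** Section 6 says of the blue-light scan: "The operator will avoid looking directly into the mouth and instead will look on the computer screen during the scanning procedure". The protocol does not say whether this operator also charted the participant or will later score the scan. After scanning, Table 1 lists only "Data selection and management".

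**Analysis.** Section 4 gives three uses of the scan data:
- An open-ended look at the data: "Exploratory analysis of the data extracted from the 3D scans will be conducted and compared to the clinical scores".
- A measure of association, namely Pearson's coefficient for scan scores against clinical ones.
- A formal test of counts: "Paired t-test will be conducted to compare the number of lesions per patient". The two methods compared are scanning and the clinical-radiographic examination.

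**Sample size.** Section 5 assumes that the new method will help dentists find more initial caries lesions than traditional methods. It uses a mean of 3.08 lesions, an SD of 1.23 and an effect of 1 lesion.

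**The concern.** A paired comparison of two detection methods can be interpreted only if neither reading is informed by the other. Here the clinical result exists before the scan does, and nothing in the plan keeps it from the person who scores the scan. A reader who knows where lesions were charted may call them on the scan more readily, which raises the scan count and the correlation.

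The second gap is the scan lesion rule. The clinical side has named criteria; the scan side has no definition of a lesion and no threshold. A lower threshold gives more scan lesions. If the rule is settled after the clinical scores have been seen, the result depends partly on that choice. If scan scores are fitted to the clinical scores, agreement is inflated and the difference in counts is pulled towards zero.

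At stake are the comparison on which the sample size rests and the second working hypothesis, that the scanner helps identify changes earlier than visual-radiographic methods.

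**Working it through.** **1. What is specified for each method**

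| Item | Clinical-radiographic | Scan |
|---|---|---|
| Criterion | ICDAS, BEWE | none stated |
| When scored | at the visit, before the scan | not stated |
| Scorer | not stated | not stated |
| Masked to the other method | charted before that visit's scan | not stated |
| Used in | correlation, paired t-test | exploration, correlation, paired t-test |

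The order of acquisition is fixed; the order and conditions of reading are not. Scoring with the chart open and scoring without it would both comply with the text.

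**2. The plan's own sample size**

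Inputs from Section 5: difference 1 lesion, SD 1.23, power 90%, significance level 5% (taken as two-sided).

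n per group = 2 × 1.23² × (1.960 + 1.282)² / 1² = 31.8, rounded up to 32. The total is 2 × 32 = 64, as stated. This is the formula for two independent groups; the figure is used below only as the number of pairs.

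**3. How sensitive the paired test is to a shift in the scan count (illustration)**

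Assumptions not in the documents: SD 1.23 for each method, between-method correlation r, no true difference, and a shift b in the mean scan count caused by the reading.

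- SD of the difference = 1.23 × √(2(1 − r)), which is 1.74, 1.23 and 0.78 for r = 0, 0.5 and 0.8.
- Noncentrality = b × √64 / SD of the difference. For b = 0.25 and r = 0.5 this is 0.25 × 8 / 1.23 = 1.63.
- Rejection rate of the two-sided 5% paired t-test with 63 degrees of freedom:

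| Shift b (lesions) | r = 0 | r = 0.5 | r = 0.8 |
|---|---|---|---|
| 0 | 5% | 5% | 5% |
| 0.10 | 7% | 10% | 17% |
| 0.25 | 20% | 36% | 72% |
| 0.50 | 62% | 89% | >99% |

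A shift well below the planned 1-lesion effect is enough to matter. The table does not show that such a shift will occur.

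**4. Why size and direction stay open**

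Assume the chart finds 60% of true lesions, so the true mean is 3.08 / 0.6 = 5.13. Let the scan alone find a share s, independently of the chart, and let a fraction k of the charted lesions missed on the scan be credited to it. Then scan count = 5.13 × (s + k × 0.6 × (1 − s)). Scan minus chart is:

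| | k = 0 | k = 0.25 | k = 0.5 |
|---|---|---|---|
| s = 0.6 | 0.00 | +0.31 | +0.62 |
| s = 0.5 | −0.51 | −0.13 | +0.26 |

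Depending on s and k, carry-over creates a difference, hides one or reverses one. The documents give neither s nor k. Fitting scan scores to clinical scores is a separate mechanism that moves the difference towards zero.

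**The case against.** The strongest reply is that a scan is a stored record. Section 4 speaks of data extracted from the scans, the Background describes overlaying scans and analysing them in software, and Table 1 puts data handling after scanning. All this is compatible with later, masked reading. The plan is silent; it does not prescribe unmasked reading. Charting first also has a merit: at baseline the scan cannot influence the clinical score. These points stand, and they rule out several stronger readings.

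- **That the comparison is biased by construction.** A reader might infer this from the sequence, but the sequence concerns acquisition only.
- **That the scan cut-off is tuned to the clinical scores.** No section says so. The exploratory comparison permits it, and the paired t-test is named separately. What is missing is the rule that produces the counts.
- **That one person charts, scans and scores.** The responsible researcher's stated tasks are information, consent, requesting radiographs and setting follow-up intervals. The study runs in two countries, and the absence of other named staff proves little.
- **That chart knowledge must produce a false scanner advantage.** If the scan alone shows 60-80% of the 3.08 charted lesions (1.85-2.46) and half of the rest are recovered, the count becomes 2.46-2.77, still below 3.08. Recovering charted lesions cannot by itself lift the scan above the chart; the scan must also find uncharted ones. Section 5 does not restrict the 3.08 to surfaces the scanner can see, so it is a weak base for such a figure in any case.

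The reply does not remove the core point: nothing in the text requires the independence that the comparison depends on.

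**Conclusion.** The point holds as a gap in the design of the reading, not as a demonstrated bias. The scans follow the charted findings, are then explored against, correlated with and tested against them, and are protected by neither masked reading nor a lesion rule fixed beforehand. The paired comparison and the correlation are therefore open to review bias.

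No size or net direction can be assigned from the documents. The rejection rates above rest on assumed shifts and correlations, on equal SDs, and on treating the counts as approximately normal. With no carry-over the shift is zero and the test keeps its level.

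This is a cheap improvement and worth making, because a chart-informed reading would compromise the comparison on which the sample size rests.

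**What to change.** State in Sections 3 and 4:

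1. **Independent reading.** For the method comparison, scan lesions are scored from coded stored scans in a later session, in random participant order, without access to the clinical or radiographic record. The scores are locked before merging. Scoring of change from overlaid scans of the same participant is a separate reading, also masked to the chart; it needs the visits together, so visit order should not be randomised there.
2. **Lesion rule.** The rule that turns scan data into a lesion is written down before any comparison with the clinical scores. If a cut-off must come from study data, derive it by cross-validation or in a random subset stratified by country. Do not derive it in one country and test it in the other: Denmark enrols ages 12-16 and Greece 18-19, so country and age would be confounded.

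**Cost.** File coding, a delayed reading session and a paragraph of text, with no extra reader, visit, procedure or participant. Research scan scores would not be available chairside. If the person who examined the participants also reads the scans, some memory may remain despite coding. A derivation subset would reduce the data left for the test.
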